4.2 Design Diagram

Study M16-126 is a Phase 3b, open-label, nonrandomized, multicenter study to evaluate the efficacy and safety of GLE/PIB in adults with chronic HCV GT5 or 6 infection, without cirrhosis or with compensated cirrhosis, who are either treatment-naïve or treatment-experienced with IFN or pegIFN with or without RBV or treatment-experienced with SOF plus RBV with or without pegIFN.

The study will enroll approximately 80 eligible subjects. A minimum of 15 GT5 and 30 GT6 subjects and up to approximately 16 subjects with compensated cirrhosis (regardless of GT) will be enrolled. Each subject will be assigned to one of two treatment arms based on their cirrhosis status. Non-cirrhotic subjects (Arm A) will be treated with GLE/PIB 300 mg/120 mg once daily for 8 weeks, while subjects with compensated cirrhosis (Arm B) will be treated with GLE/PIB 300 mg/120 mg once daily for 12 weeks.

Scheduled visits for subjects in the Treatment Period consist of Day 1 and Weeks 1, 2, 4, and 8 for all subjects and an additional Week 12 visit for subjects in Arm B. Subjects who complete or prematurely discontinue study drug will be followed for 24 weeks. During the Post-Treatment Period, all subjects will have visits at Post-Treatment Weeks 4, 12, and 24.

Figure 1. Study Schematic

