The number and percentage of subjects with laboratory values meeting the following criteria during treatment will be summarized:

- Post-nadir (preceding value is lower than the subsequent value) ALT $> 5 \times \text{ULN}$ (regardless of grade change);
- Total bilirubin $\geq 2 \times \text{ULN}$ and $>$ baseline (i.e., a post-baseline value must be more extreme than the baseline value to be considered);
- Post-nadir ALT $> 3 \times \text{ULN}$ and total bilirubin $> 2 \times \text{ULN}$;
- Post-nadir ALT $> 3 \times \text{ULN}$ and total bilirubin $\leq 2 \times \text{ULN}$.

Four listings (one for each bullet above) of all hepatic laboratory values including ALT, AST, total, indirect and direct bilirubin, ratio of direct to total bilirubin, and alkaline phosphatase values will be provided for each subject who met the criterion defined above.

Hepatic Laboratory Abnormalities of Interest

Among the events assessed under "Assessment of Hepatic Laboratory Values," the following criteria are of interest:

- Confirmed post-nadir ALT $> 5 \times \text{ULN}$;
- Post-nadir ALT $> 3 \times \text{ULN}$ and a concurrent total bilirubin $> 2 \times \text{ULN}$ with a direct/total bilirubin ratio > 0.4 .

To support the assessment of hepatic laboratory abnormalities of interest, the following potential events will be summarized:

- Confirmed post-nadir ALT $> 5 \times \text{ULN}$;
- Post-nadir ALT $> 3 \times \text{ULN}$ and total bilirubin $> 2 \times \text{ULN}$ and direct/total bilirubin ratio > 0.4 .

Two listings (one for each bullet) of all hepatic laboratory values including ALT, AST, total, indirect and direct bilirubin, ratio of direct to total bilirubin, and alkaline phosphatase values will be provided for each subject who met the criterion defined above.

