For the **assessments of hepatic laboratory values** and **hepatic laboratory abnormalities of potential interest**, the maximum ratio relative to the ULN will be used to determine if subjects meet any of the criteria listed above. The ALT and total bilirubin values do not need to be concurrent in order to meet the defined criteria in statistical summaries. For ALT, the post-baseline value must represent an increase from the first nadir (including baseline) to be counted. First nadir is defined as the last value prior to the first increase. For total bilirubin, a subject will be counted if the post-baseline laboratory value meets the above criteria regardless of the baseline laboratory value (i.e., the post-baseline laboratory value does not need to be worse than the baseline laboratory value), except where noted above. A confirmed post-nadir increase in ALT is defined as two consecutive values of $ALT > 5 \times ULN$ after nadir, either both during treatment or at the final treatment measurement and the next consecutive post-treatment measurement. A single post-nadir ALT value of greater than $5 \times ULN$ followed by lost to follow-up (no additional ALT values) also will be considered (i.e., will not require confirmation). The ratio of direct to total bilirubin will be calculated using the same date/time sample corresponding to the total bilirubin elevation.

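### SAP 11.3.2 words post-nadir ALT in two ways and leaves the confirming rule open, so a confirmed flare in a subject entering above 5 x ULN can drop out of the confirmed count

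*SAP*

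**What the plan says.** All the relevant text is in SAP 11.3.2 (Statistical Methods for laboratory data).

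- Under Assessment of Hepatic Laboratory Values, the first criterion (> 5 x ULN, regardless of grade change) carries a short gloss: "Post-nadir (preceding value is lower than the subsequent value) ALT". This compares each value with the one before it.
- The closing paragraph, which covers both the hepatic assessments and the abnormalities of interest, sets a different comparison: "For ALT, the post-baseline value must represent an increase from the first nadir (including baseline) to be counted". It continues: "First nadir is defined as the last value prior to the first increase". No minimum rise is required, and there is no reset if ALT later falls lower.
- Confirmation is worded separately. "A confirmed post-nadir increase in ALT is defined as two consecutive values of" ALT above 5 x ULN after nadir, both on treatment or spanning the final treatment sample and the next post-treatment one. Whether each value must exceed the first nadir, or only come later in time, is not stated.
- Subjects are classified on their largest value: "the maximum ratio relative to the ULN will be used to determine if subjects meet any of the criteria listed above".
- Each subject who meets one of the four assessment criteria is listed in full: "Four listings (one for each bullet above) of all hepatic laboratory values including ALT, AST, total, indirect and direct bilirubin", with further hepatic tests.

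Confirmed post-nadir ALT > 5 x ULN is one of two hepatic laboratory abnormalities of interest.

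**The concern.** A nadir fixed before the first upward step is a poor reference for subjects who enter with high ALT. If ALT ticks up slightly at Week 1, the first nadir is the baseline value itself. ALT can then fall to normal and flare, and the flare is still judged against the high entry value.

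Protocol 5.2.2 excludes ALT only above 10 x ULN, so baselines between 5 and 10 x ULN are eligible. Safety is a primary objective, and the confirmed criterion is the stricter of the two ALT > 5 x ULN summaries. Two programmers working from the same text could report different confirmed counts from the same data.

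**Working it through.** The documents give no figure for this rule, so there is none to reproduce. The check applies the wordings to example series and then to a full grid.

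**Inputs.** Cut-offs of 5 and 3 x ULN (SAP 11.3.2); ALT up to 10 x ULN at screening (protocol 5.2.2); sampling times from SAP 4.2: "Scheduled visits for subjects in the Treatment Period consist of Day 1 and Weeks 1, 2, 4, and 8 for all subjects", plus Week 12 in Arm B and Post-Treatment Week 4. In Arm A this gives six scheduled values, the last of which can confirm the Week 8 value.

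**Unconfirmed criteria.** Let N be the first nadir, R the first rise (so R > N), and V a later value above cut-off c that exceeds its predecessor.

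- If V > N, both wordings count the subject.
- If V ≤ N, then R > N ≥ V > c, so R already counts the subject under both wordings.
- Conversely, suppose a subject is counted under the first-nadir wording. If N > c, R is itself a rise above c. If N ≤ c, some value must cross c upward, and it exceeds its predecessor. The preceding-value wording counts the subject either way.

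Subject-level results are therefore identical. The same holds for the ALT > 3 x ULN criteria paired with bilirubin as they are summarised, because "The ALT and total bilirubin values do not need to be concurrent in order to meet the defined criteria in statistical summaries". A version requiring concurrent values was not checked.

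**Confirmed criterion.** Readings, each requiring two consecutive values > 5 x ULN:

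1. the first value exceeds its predecessor;
2. both values exceed their predecessors;
3. the pair is merely later than the first nadir;
4. the first value exceeds the first nadir;
5. both values exceed the first nadir;
6. both values exceed the lowest earlier ALT (the proposal below).

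| Series (x ULN) | First nadir | 1 | 2 | 3 | 4 | 5 | 6 |
|---|---|---|---|---|---|---|---|
| 8.0, 8.2, 3.0, 0.9, 7.0, 7.6 | 8.0 | yes | yes | yes | **no** | **no** | yes |
| 8.0, 7.8, 3.0, 0.9, 7.0, 7.6 | 0.9 | yes | yes | yes | yes | yes | yes |
| 4.0, 4.2, 3.0, 0.9, 7.0, 7.6 | 4.0 | yes | yes | yes | yes | yes | yes |
| 8.0, 8.2, 3.0, 0.9, 9.0, 9.6 | 8.0 | yes | yes | yes | yes | yes | yes |
| 10, 6.0, 6.1, 6.1, 4, 2 | 6.0 | yes | no | yes | yes | yes | yes |

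Rows 1 and 2 contain the same flare, from 0.9 to 7.6 (7.6/0.9 = 8.4-fold). Under readings 4 and 5, a Week 1 value of 8.2 rather than 7.8 decides whether it is confirmed.

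**When a flare is lost.** If N ≤ 5, every value above 5 exceeds N and nothing is lost. So N > 5 is necessary. Values do not rise before N, so baseline ≥ N > 5 as well. The flare must also fail to stay above N (compare rows 1 and 4).

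**Grid.** Baselines 1 to 10 and four later values of 1 to 12, all integers, give 10 x 12^4 = 207,360 series.

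- Unconfirmed criteria: 0 discordant between the two wordings, at 5 and at 3 x ULN.
- Confirmed, against reading 1: reading 3 differs in 0 series, reading 4 drops 1,750, reading 5 drops 11,082; none adds any. Every dropped series still meets the unconfirmed > 5 x ULN criterion.
- Confirmed, against reading 6: reading 5 misses 3,161 and adds none; reading 4 misses 1,750 and adds 7,921.

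These are counts on an artificial grid, not patient rates.

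**Other outputs, row 1.** Baseline 8.0 and the later 8.2, 7.0 and 7.6 are all Grade 3 in SAP Table 9 (> 5 to 20 x ULN). The maximum-grade table requires a grade worse than baseline, so it does not count this subject. The unconfirmed > 5 x ULN criterion does, through 8.2 at Week 1.

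**The case against.** The strongest reply is that the preceding-value phrase is only a gloss, the closing paragraph is the operative rule, and its confirmation sentence says after nadir, which can be read as time alone. On that reading (3) no flare is lost. This stands as a possible reading. But the same paragraph says a value must be an increase from the first nadir to be counted, and reading 3 gives that sentence no effect on the confirmed count. The text does not settle the matter.

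A reader might infer more than the documents support:

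- *That the wordings conflict throughout.* They give identical subject-level results for the unconfirmed criteria.
- *That the flare is discarded.* At most the confirmed label is lost. The subject still meets the > 5 x ULN criterion regardless of grade change, and all hepatic values, including the fall and the rebound, are listed.
- *That any small early rise causes the problem.* It takes a first nadir above 5 x ULN and a flare that does not stay above it.
- *That the first-nadir rule is what makes improving subjects count.* In the series 10, 6.0, 6.1, 6.1, ALT has risen by 0.1/6.0 = 1.7% and is 39% below baseline, yet it is confirmed under readings 1, 3, 4, 5 and 6. Reading 2 rejects it only because the last two values are equal; 6.0, 6.1, 6.2 would pass.

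**Conclusion.** The point holds in a narrow form. SAP 11.3.2 has two wordings for post-nadir ALT and leaves open whether confirming values must exceed the nadir. If the first-nadir sentence is applied to them, a subject entering above 5 x ULN can fall to normal, have two consecutive values > 5 x ULN, and not enter the confirmed count.

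The effect is confined to that one count. With about 80 subjects, one such case is 1/80 = 1.25 percentage points. That is the size of one misclassification, not an estimate of how likely it is: the documents do not give the share of subjects with baseline ALT above 5 x ULN. Nor do they support saying that the safety conclusion could change, since no hypothesis is tested and no decision rule is attached to this count. Minor severity.

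**What to change.** Use one definition in both places in SAP 11.3.2. Define nadir as the lowest ALT from baseline through the sample before the value being assessed. State that both confirming values must be > 5 x ULN and above that nadir. This confirms the 0.9 to 7.6 flare whatever happened at Week 1.

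This definition, too, counts trivial rises at a still-elevated level, such as 10, 6.0, 6.1, 6.1. Add a descriptive row for ALT > 5 x ULN and > 2 x baseline, the criterion already in protocol 6.1.7.1, as an analysis output only; it changes no clinical rule. That series does not meet it (6.1 against 2 x 10 = 20). Nor does the row 1 flare (7.6 against 2 x 8.0 = 16), so the row supplements the nadir definition and cannot replace it.

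The cost is SAP wording and a small change to the project-standard program; no new data are needed. Some comparability with other studies in the project is lost, which can be handled by keeping the current definition as a secondary row, with its confirming rule spelled out.

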11.4 Analysis of Vital Signs and Weight

11.4.1 Variables and Criteria Defining Abnormality

Vital sign variables are body temperature, sitting systolic blood pressure, sitting diastolic blood pressure, sitting pulse rate, and body weight.

The criteria for Potentially Clinically Significant (PCS) vital sign findings are presented in [Table 10](#).

Table 10. Criteria for Potentially Clinically Significant Vital Sign Values

Test/Measurement	Very Low (VL)	Very High (VH)
Systolic Blood Pressure	≤ 90 mmHg AND A decrease of ≥ 20 mmHg from baseline	≥ 180 mmHg AND An increase of ≥ 20 mmHg from baseline
Diastolic Blood Pressure	≤ 50 mmHg AND A decrease of ≥ 15 mmHg from baseline	≥ 105 mmHg AND An increase of ≥ 15 mmHg from baseline
Pulse Rate	≤ 50 bpm AND A decrease of ≥ 15 bpm from baseline	≥ 120 bpm AND An increase of ≥ 15 bpm from baseline
Weight	A decrease of $\geq 15\%$ from baseline	An increase of $\geq 15\%$ from baseline
Body Temperature		$> 38.3^{\circ}\text{C}$ AND An increase of $\geq 1.1^{\circ}\text{C}$ from baseline

11.4.2 Statistical Methods

The baseline value for vital signs will be the last measurement on or before the day of the first dose of study drug. The same baseline value will be used for changes to Treatment Period visits and changes to Post-Treatment Period visits.

For each vital sign parameter listed in Section 11.4.1, values at each visit (baseline and post-baseline, including applicable post-treatment visits) will be summarized with the sample size, mean, standard deviation, minimum, median, and maximum.

The number and percentage of subjects with on-treatment values meeting the specified criteria for PCS vital sign values (Table 10) will be summarized. A post-baseline value must be more extreme than the baseline value to be considered a PCS finding. A separate listing will be provided that presents all vital sign values for the subjects meeting PCS criteria during treatment.

12.0 Summary of Changes

12.1 Summary of Changes Between the Latest Version of the Protocol and SAP Version 1.0

1. New expected confidence intervals are calculated in Section 4.3 Sample Size because the rule of choosing between the normal approximation method and

Wilson's score method for the primary endpoint has been updated in the protocol (also see Section 10.3)

2. All safety analyses have been changed to be performed only for the overall population because integrated safety analyses on Phase 3 studies showed no difference in safety profiles between subjects with compensated cirrhosis and without cirrhosis.
3. The race category of Black/non-Black has been changed to Asian/non-Asian in Section 7.1 and Section 10.6 because the Asian population is of interest to this study while very few Black subjects are expected to enroll. Also, different Asian types will be summarized among the baseline characteristics (Section 7.1).
4. The category of baseline HCV RNA level has been changed from 6,000,000 IU/mL to 2,000,000 IU/mL because it is a better cutoff based on previous studies.
5. Efficacy endpoints will also be summarized for the overall population (Section 10.6, Section 10.7 and Section 10.9) in order to provide results across all subjects in the study.
6. The integrated efficacy analysis combining GT5 and GT6 subjects from Studies M14-868 Part 4, M14-172 and M16-126 using meta-analytic methods has been removed because there is no plan for a label update with such data.
7. The resistance analyses (Section 10.8) have been updated to reflect current HCV project standards.
8. Text in PRO analyses of mean change from baseline has been updated for better clarity (Section 10.9).
9. Missing data handling conventions for scores related to the Work Productivity and Activity Impairment Questionnaire (WPAI) – Hepatitis C are specified in Section 10.9.
10. Methods for the assessment of hepatic laboratory values and hepatic laboratory abnormalities of interest have been added to Section 11.3.2 to reflect current HCV project standards.

11. The summaries of changes from baseline for vital signs have been replaced with summaries of visit values to reflect current HCV project standards (Section 11.4.2).

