Change from baseline to each applicable visit in the patient reported outcome summary measures will be summarized.

Safety:

Safety summaries will be provided by the treatment arm (i.e., cirrhosis status/study drug duration) and overall. All subjects who receive at least one dose of study drug will be included in the safety analyses. Adverse events will be coded using the Medical Dictionary for Regulatory Activities (MedDRA). The number and percentage of subjects with treatment-emergent adverse events (i.e., any event that begins or worsens in severity after initiation of study drug) will be tabulated by MedDRA System Organ Class (SOC) and preferred term. The tabulation of the number of subjects with treatment-emergent adverse events also will be provided by grade and relationship to study drug. Change from baseline in laboratory tests and vital signs measurements to each time point of collection will be summarized, and values that are potentially clinically significant, according to predefined criteria, will be summarized by treatment arm (i.e., cirrhosis status/study drug duration) and overall. Changes from baseline to post-baseline in the CTCAE grading of laboratory values will also be summarized.

Pharmacokinetic:

Plasma concentrations of glecaprevir and pibrentasvir will be tabulated for each subject and treatment arm. Summary statistics will be computed for each treatment arm. Population pharmacokinetic analyses will be performed using the actual sampling time relative to dosing. Pharmacokinetic models will be built using a non-linear mixed-effect modeling approach.

Resistance:

For all subjects receiving study drug, the variants at signature resistance-associated amino acid positions at baseline identified by next generation sequencing (NGS) and comparison to the appropriate prototypic reference sequence will be analyzed.

The following resistance information will be analyzed for subjects receiving study drug who do not achieve SVR₁₂ and who have a post-baseline sample with HCV RNA \geq 1000 IU/mL: 1) the amino acid variants in available post-baseline samples identified by NGS and comparison to the baseline sequences, 2) the amino acid variants in available post baseline samples at signature resistance-associated positions identified by NGS, and comparison to the appropriate prototypic reference sequence, and 3) the persistence of viral resistance by NGS.

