8.1.5.3 Vital Signs Data

Mean changes in temperature, systolic and diastolic blood pressure, pulse, and weight from baseline to each post-baseline visit, including final treatment visit, will be summarized. The number and percentage of subjects with post-baseline values meeting pre-defined criteria for PCS (Potentially Clinically Significant) vital signs values during treatment will be summarized.

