6.2 Definition of Analysis Windows

For efficacy analyses of HCV RNA and resistance, the time windows specified in [Table 1](#) and [Table 2](#) describe how these data are assigned to protocol-specified time points during the Treatment and Post-Treatment Periods, respectively. All time points and corresponding time windows are defined based on the date/time of blood sample collection.

For safety laboratory data, patient reported outcome (PRO) data and vital sign data, the time windows specified in [Table 1](#) and [Table 3](#) describe how data are assigned to protocol-specified time points.

If more than one assessment is included in a time window, the assessment closest (except for when used in analyses of SVR) to the nominal time will be used. If there are

two observations equally distant to the nominal time, the latest one will be used in analyses. For analyses of SVR (e.g., SVR₁₂), the last value in the window will be used.

If multiple measurements are made on the same day for a safety laboratory parameter or a vital sign parameter, the average of the values will be used to calculate descriptive statistics and in analyses of the mean change from baseline. For summaries of shifts from baseline and potentially clinically significant values, multiple values on the same day will not be averaged; all values will be considered for these analyses.

Table 1. Analysis Time Windows for HCV RNA, Resistance Endpoints, Safety Laboratory, Vital Sign Measurements, and PRO Instruments (Treatment Period)

Scheduled Visit	Nominal Day (Study Day)	Time Window (Study Day Range)
Day 1/Baseline ^a	1	≤ 1 ^a
Week 1	7	2 to 10
Week 2	14	11 to 21
Week 4	28	22 to 42
Week 8	56	43 to 70
Week 12 ^b	84	71 to 98
Final Treatment Visit ^c	2 to ≤ 2 days after last dose of study drug	

a. Day of first dose of study drug.

b. For Arm B only.

c. The last value within the window will be used to define the Final Treatment Visit value. The upper bound of this Final window is Study Drug End Day 2. Study Drug End Day 0 is defined as the day of the last dose of study drug.

Note: For all windows, data must be on or before Study Drug End Day 2. The result closest to the scheduled time point will be used. PRO instruments are collected at Day 1 Visit and End of Treatment Visit (Week 8 for Arm A and Week 12 for Arm B, or Premature Discontinuation Visit).

Table 2. Analysis Time Windows for HCV RNA and Resistance Endpoints (Post-Treatment Period)

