11.3.2 Statistical Methods

The baseline value for clinical laboratory tests will be the last non-missing measurement on or before the day of the first dose of study drug. Values on Day 1 must also be before the time of first dose if time is available. The same baseline value will be used for changes to Treatment Period visits and changes to Post-Treatment Period visits.

Visit Values

For each laboratory parameter listed in Section 11.3.1, values at each visit (baseline and post-baseline, including applicable post-treatment visits) will be summarized with the

sample size, mean, standard deviation, minimum, median, and maximum. Figures presenting mean values over time will be produced.

Change from Baseline

For each laboratory parameter listed in Section 11.3.1, changes from baseline to each post-baseline visit, including applicable post-treatment visits, will be summarized with the sample size, baseline mean; visit mean; and change from baseline mean, standard deviation, minimum, median, and maximum.

Shift Tables

Individual changes in the laboratory parameters listed in Section 11.3.1 will be tabulated using shift tables. Laboratory data values will be categorized as low, normal, or high based on normal ranges of the laboratory used for each sample. Shift tables from baseline to minimum value and maximum value during the Treatment Period will be created. For each parameter, the shift tables will cross tabulate the frequency of subjects with baseline values below/within the normal range to maximum above the normal range and with baseline values within/above the normal range to minimum below the normal range.

Maximum Toxicity Grade

The laboratory parameters listed in Table 9 will be assigned a toxicity grade of 1, 2, 3, or 4. The number and percentage of subjects with a maximum toxicity grade of 1, 2, 3 or 4 during the Treatment Period will be tabulated. To be counted, the post-baseline value must have a toxicity grade that is more extreme than the toxicity grade corresponding to the baseline value. For each laboratory parameter in Table 9, the summary will also include the number and percentage of subjects with a maximum of at least Grade 3. A listing of all relevant laboratory parameters will be provided for each subject who had an increase to Grade 2 or higher for any laboratory variable in Table 9.

Assessment of Hepatic Laboratory Values

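### The SAP drops the protocol's change-from-baseline summaries for vital signs, so no output shows the spread of within-subject change and the pooled Week 12 mean cannot be compared with baseline

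*SAP*

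**What the plan says.** Protocol 8.1.5.3 commits to summarising "Mean changes in temperature, systolic and diastolic blood pressure, pulse, and weight from baseline to each post-baseline visit", and it includes the final treatment visit. The synopsis makes the same commitment: "Change from baseline in laboratory tests and vital signs measurements to each time point of collection will be summarized".

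SAP 11.4.2 provides something different. For each vital-sign parameter, "values at each visit (baseline and post-baseline, including applicable post-treatment visits) will be summarized with the sample size, mean, standard deviation", together with the minimum, median and maximum. No change statistic follows. Item 11 of SAP 12.1 confirms that this is deliberate: "The summaries of changes from baseline for vital signs have been replaced with summaries of visit values to reflect current HCV project standards". No other reason is given.

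Three other places bear on the point:

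- SAP 11.4.2 still defines a baseline for changes: "The same baseline value will be used for changes to Treatment Period visits and changes to Post-Treatment Period visits". SAP 6.2 still has a same-day rule, covering vital signs as well as laboratory data, under which "the average of the values will be used to calculate descriptive statistics and in analyses of the mean change from baseline".
- For laboratory data, SAP 11.3.2 keeps both kinds of summary. Besides visit values, "changes from baseline to each post-baseline visit, including applicable post-treatment visits, will be summarized with the sample size, baseline mean; visit mean", followed by the mean, SD and range of the change.
- SAP 5.1.3 and 11.1 pool all safety summaries over arms. Item 2 of 12.1 records this as a departure from the protocol, which in 8.1.5 asks for safety summaries by arm and overall.

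**The concern.** Safety is one of the primary objectives and the trial has no control arm, so how far subjects move from their own baseline is the natural description of vital signs. With visit values only, a reader who wants the change must subtract one mean from another. This has two weaknesses.

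First, the spread of change cannot be recovered. Two visit SDs do not determine the SD of the difference without the correlation between visits, and that is not reported.

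Second, the subtraction describes a change only if the same subjects stand behind both means. Pooling over arms breaks this condition at Week 12 even with perfect attendance. An apparent shift in weight or blood pressure could then reflect who was measured, and a real shift could be masked in the same way.

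**Working it through.** The plan states no figure for vital signs, so there is none to reproduce. The inputs are its visit schedule and its enrolment numbers.

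**Inputs from the documents**

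- Total enrolment N is about 80, with up to about 16 cirrhotic subjects (Protocol 8.2, SAP 4.2). All cirrhotic subjects are in Arm B.
- Week 12 applies to Arm B only (SAP 6.2, Table 1, note b). Weeks 1, 2, 4 and 8 and all post-treatment visits apply to everyone (SAP 4.2).
- Vital signs are pooled over arms (SAP 11.1).

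Baseline differences between groups of subjects are not given. Those used below are assumptions.

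**Step 1: same subjects at both visits.** The difference of the two visit means equals the mean of the individual differences. It is the same estimate with the same sampling variance. What the table lacks is the SD, minimum, median and maximum of those differences.

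**Step 2: Week 12.** Let A and B be the baseline means of the two arms and n_B the size of Arm B, and suppose all of Arm B attend Week 12.

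- Overall baseline mean = (1 − n_B/N) × A + (n_B/N) × B.
- Week 12 mean minus overall baseline mean = (true mean change in Arm B) + (1 − n_B/N) × (B − A).
- With n_B = 16 and N = 80, the multiplier is 1 − 16/80 = 0.8.

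| Assumed B − A (kg or mmHg) | Apparent change with nobody changing |
|---|---|
| 0 | 0 |
| 5 | 0.8 × 5 = 4 |
| 10 | 0.8 × 10 = 8 |

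The sign follows the sign of B − A. The 16 is a ceiling, and a smaller Arm B makes the multiplier larger: with 8 of 80 it would be 1 − 8/80 = 0.9.

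**Step 3: missed visits.** If k of N subjects miss a visit and their baseline mean differs by d from that of the rest, the visit mean departs from the full baseline mean by k × d/N, with nobody changing.

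- k = 4, d = 20 kg: 4 × 20/80 = 1.00 kg.
- k = 4, d = 10 kg: 4 × 10/80 = 0.50 kg.

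**Step 4: what else is planned.** The counts of potentially clinically significant (PCS) values are relative to baseline: "A post-baseline value must be more extreme than the baseline value to be considered a PCS finding". But Table 10 sets extreme limits, for example a weight change of 15% or more, or systolic pressure of at least 180 mmHg together with a rise of at least 20 mmHg. The vital-sign listing covers only subjects who meet those criteria. Neither output gives the centre or spread of change.

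**The case against.** The departure is declared, located and given a reason. The output is descriptive: neither document plans a test or confidence interval for vital signs, and no formal hypothesis is tested. The data are collected anyway, so a change table could be produced later. Most visits are scheduled for every subject, and the table will show the sample size at each visit, so a careful reader would see the drop at Week 12. Within-subject assessment is not absent either. Every criterion in Table 10 involves change from baseline, and Protocol 6.1.1.1 captures vital-sign changes as adverse events when they lead to discontinuation, need intervention or are judged adverse by the investigator. All of this stands, and it keeps the point minor.

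The missed-visit figure is also weak evidence on its own. A 20 kg gap is large: with an assumed weight SD of 15 kg, the standard error of a difference between 4 and 76 subjects is 15 × sqrt(1/4 + 1/76) = 7.7 kg, so 20 kg is about 2.6 standard errors.

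A reader might infer something stronger, that reporting visit means makes the mean change much less precise, by comparing a standard error for two independent samples with a paired one. The documents do not support that. By Step 1, when the same subjects attend both visits the estimate and its true variance are identical. The larger standard error arises only if someone wrongly treats the visits as independent, and no such calculation is planned.

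What the objection does not answer is Week 12. A visible sample size warns the reader but does not supply the Arm B baseline mean or the paired change.

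**Conclusion.** The point holds as a minor one. SAP 11.4.2 removes a summary that the protocol specifies in two places, and the reason given is project standards rather than anything specific to this trial. The SD and range of within-subject change are lost for every vital sign. At Week 12 the pooled table sets a baseline mean over about 80 subjects beside a mean over at most about 16 cirrhotic subjects, and the difference is not a change in any set of subjects. The displacement is 0.8 times the baseline difference between arms.

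The multiplier follows from the planned numbers, with Arm B at its ceiling and attending in full. The 4 kg or 4 mmHg illustration rests on an assumed difference of 5, and if the arms are alike at baseline the displacement is nil. The 1.00 kg missed-visit figure rests wholly on assumed values.

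A reader might also take the mean change from baseline as a drug effect. Without a control arm it is not one, whether paired or not. The case for restoring it is accurate description.

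**What to change.** In SAP 11.4.2, keep the visit values and add, for each vital-sign parameter, change from baseline to each post-baseline visit and to the Final Treatment Visit. Report n, the baseline mean of subjects with both values, the visit mean, and the mean, SD, minimum, median and maximum of change. This follows the laboratory layout in 11.3.2, but two elements need to be written out because 11.3.2 does not state them: the restriction of the baseline mean to subjects with both values, and the Final Treatment Visit.

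Delete item 11 of SAP 12.1. The wording on changes in SAP 6.2 and 11.4.2 then applies as it stands.

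The cost is a short SAP edit and reuse of the laboratory change-table program. No new data are needed.
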